## CONSENT PROCEDURES

Explain in detail how, when, where, and by whom consent is obtained, and the timing of consent (i.e., how long subjects will be given to consider participation). For most studies involving more than minimal risk and all studies involving investigational drugs/devices, a licensed physician investigator must obtain informed consent. When subjects are to be enrolled from among the investigators' own patients, describe how the potential for coercion will be avoided.

Parent/guardian consent and child assent will be obtained after describing the purpose of the study and its requirements to the subjects and their parents/guardians, and prior to performing any procedures. Per institutional guidelines, those study volunteers who are 14 -17 years will document their written assent on the same PHRC approved consent form as their parents/guardians. The permission of one parent/guardian will be sufficient to document on the consent form. The consent form will be signed in the presence of a licensed physician or psychologist investigator or study nurse practitioner. Psychologists obtaining consent will hold a PhD or PsyD degree, be licensed to practice psychology in Massachusetts, and be listed as co-investigators on study staff. When consent is being obtained by a nurse practitioner or clinical psychologist, an optional consultation with a licensed physician investigator must be offered to all potential subjects before they sign the consent form. This offer, and its acceptance or refusal by the potential subject, must be documented in the research record. Any issues or problems with

the consent process must be reported to the PHRC as they occur, as “Other Event,” not logged and held for continuing review. Subjects will have up to 6 weeks to consider participation. Minor subjects who turn 18 years of age during the course of the study will be asked to sign the approved consent form as an adult.

In cases where the parents live out of state and find it difficult or inconvenient to come to Boston, we will ask the IRB for an exception to the protocol such that the study can be explained to parents and subjects over the phone and consent forms mailed/faxed to the parents/subjects to sign and send back to us. The consent interview will be conducted by telephone when the parent can read the consent as it is discussed.

NOTE: When subjects are unable to give consent due to age (minors) or impaired decision-making capacity, complete the forms for Research Involving Children as Subjects of Research and/or Research Involving Individuals with Impaired Decision-making Capacity, available on the New Submissions page on the PHRC website:

<http://healthcare.partners.org/phsirb/newapp.htm#Newapp>

For guidance, refer to the following Partners policy:

Informed Consent of Research Subjects

<http://healthcare.partners.org/phsirb/infcons.htm>

## DATA AND SAFETY MONITORING

Describe the plan for monitoring the data to ensure the safety of subjects. The plan should include a brief description of (1) the safety and/or efficacy data that will be reviewed; (2) the planned frequency of review; and (3) who will be responsible for this review and for determining whether the research should be altered or stopped. Include a brief description of any stopping rules for the study, when appropriate. Depending upon the risk, size and complexity of the study, the investigator, an expert group, an independent Data and Safety Monitoring Board (DSMB) or others might be assigned primary responsibility for this monitoring activity.

NOTE: Regardless of data and safety monitoring plans by the sponsor or others, the principal investigator is ultimately responsible for protecting the rights, safety, and welfare of subjects under his/her care.

Unanticipated problems or adverse events involving risks to subjects that are related to the study or study drugs will be reported within 5 working days or 7 calendar days of the date the study investigator becomes aware of the problem per PHRC guidelines. Mild and moderate adverse events will be reported to the Partners IRB per guidelines.

Data Safety Monitoring Board: One central Data Safety Monitoring Board (DSMB) will be convened at MGH every six months to review all adverse events at both sites. Moreover, additional meetings may be called to consider urgent issues. The following personnel have served on the DSMB for the current grant for the past 5 years and have agreed to continue to serve on the DSMB:

- [name]. Instructor of Psychology, Harvard Medical School. Staff Psychologist, Massachusetts General Hospital for Children
- [name], MD, Pediatric Endocrine Unit, Massachusetts General Hospital
- [name]., Pediatric Endocrine Unit, Massachusetts General Hospital

- [name], Sc.D., Biostatistician, Biometrics Center, Beth Israel Deaconess Medical Center, Instructor in Medicine, Harvard Medical School
- [name], RD., LDN, CNSC, Nutrition and Food Services, Massachusetts General Hospital

Serious Adverse Events that are related to the study or study drugs will be telephoned into MGH within one working day, and forms faxed or mailed within 72 hours. These events will be promptly related to the IRB and FDA by the Study Coordinator. If the Data and Safety Monitoring Board wishes to be notified, we will initiate this notification as well.

Describe the plan to be followed by the Principal Investigator/study staff for review of adverse events experienced by subjects under his/her care, and when applicable, for review of sponsor safety reports and DSMB reports. Describe the plan for reporting adverse events to the sponsor and the Partners' IRB and, when applicable, for submitting sponsor safety reports and DSMB reports to the Partners' IRBs. When the investigator is also the sponsor of the IND/IDE, include the plan for reporting of adverse events to the FDA and, when applicable, to investigators at other sites.

**NOTE:** In addition to the adverse event reporting requirements of the sponsor, the principal investigator must follow the Partners Human Research Committee guidelines for Adverse Event Reporting

Serious Related Adverse Events will be reported within 10 days per PHRC guidelines. These events will be promptly related to the IRB and FDA by the Study Coordinator. Mild and moderate adverse events will be reported to the Partners IRB per guidelines. All adverse events will also be reviewed every six months during the DSMB meetings.

## MONITORING AND QUALITY ASSURANCE

Describe the plan to be followed by the principal investigator/study staff to monitor and assure the validity and integrity of the data and adherence to the IRB-approved protocol. Specify who will be responsible for monitoring, and the planned frequency of monitoring. For example, specify who will review the accuracy and completeness of case report form entries, source documents, and informed consent.

**NOTE:** Regardless of monitoring plans by the sponsor or others, the principal investigator is ultimately responsible for ensuring that the study is conducted at his/her investigative site in accordance with the IRB-approved protocol, and applicable regulations and requirements of the IRB.

**Specimens:** Blood specimens and all other testing will be obtained from subjects for research purposes only. From the study visits, most blood samples will be frozen and stored in freezers in the Neuroendocrine Unit of Massachusetts General Hospital. These freezers are accessible to no one but the Neuroendocrine staff. Some blood samples will be sent to the chemistry laboratories of MGH for analysis, and left over samples will be disposed of as per institutional guidelines.

The privacy of subjects and confidentiality of data obtained from subjects will be maintained strictly. In any reports or publications resulting from the study, the privacy and anonymity of individuals in the report will be protected. The subject's name will be removed as markers on any clinical reports submitted as attachments to an adverse event report. Subjects will be assigned a code, which will be used in all data used for analysis.

**Adverse Events:** Serious Related Adverse Events will be reported within 10 days per PHRC guidelines. These events will be promptly related to the IRB and FDA by the Study Coordinator. Mild and moderate adverse events will be reported to the Partners IRB per guidelines. All adverse events will also be reviewed every six months during the DSMB meetings.

**Data Quality Control:** All data will be recorded on specified Case Report Forms. Completed forms will be sent to Massachusetts General Hospital and retained at the remote site. As forms are received at Massachusetts General Hospital, they will be logged into a forms calendar, which contains all subjects' code numbers and dates of each follow-up visit. In our experience, this has facilitated an easy, accurate, and global check of each subject's status, as well as providing recruitment and drop-out information. After each form is logged, it will be carefully checked for legibility and completeness and for ambiguity. Data from the forms, including laboratory results, will be entered into an electronic database. Forms that have missing or inconsistent data will also be entered into the database, except that a missing value indicator will take the place of the missing or inconsistent information. A missing information form will be filled out to indicate the items that are missing.

Forms that are complete will be filed in a dedicated locked filing cabinet organized by subject code number. Forms that have missing data will be kept separately for ease of notifying coordinators.

Accuracy of data entry will be checked using different methods at the beginning of the study and later when site monitoring has started. At the start of the study, before the first site monitoring data is returned, the coordinator will check 100 random data items on the database against the case records each month. If the error rate of data entry is worse than 2.5% overall or appears in crucial variables we will consider that a "data entry problem" exists and initiate whatever corrective action is necessary. One corrective action would be to initiate double entry of all data.

For guidance, refer to the following Partners policies:

Data and Safety Monitoring Plans and Quality Assurance

<http://healthcare.partners.org/phsirb/datasafe.htm>

Adverse Event Reporting Guidelines

[http://healthcare.partners.org/phsirb/adverse\\_events.htm](http://healthcare.partners.org/phsirb/adverse_events.htm)

## PRIVACY AND CONFIDENTIALITY

Describe methods used to protect the privacy of subjects and maintain confidentiality of data collected. This typically includes such practices as substituting codes for names and/or medical record numbers; removing face sheets or other identifiers from completed surveys/questionnaires; proper disposal of printed computer data; limited access to study data; use of password-protected computer databases; training for research staff on the importance of confidentiality of data, and storing research records in a secure location.

NOTE: Additional measures, such as obtaining a Certificate of Confidentiality, should be considered and are strongly encouraged when the research involves the collection of sensitive data, such as sexual, criminal or illegal behaviors.

Most blood samples will be frozen and stored in freezers in the Neuroendocrine Unit of Massachusetts General Hospital. These freezers are accessible to no one but the Neuroendocrine staff. Some blood samples will be sent to the chemistry and hematology laboratories of MGH for analysis, and left over samples will be disposed of as per institutional guidelines.

The privacy of subjects and confidentiality of data obtained from subjects will be maintained strictly. In any reports or publications resulting from the study, the privacy and anonymity of individuals in the report will be protected. The subject's name will be removed as markers on any clinical reports submitted as attachments to an adverse event report. Subjects will be assigned a code, which will be used in all data used for analysis.

### **SENDING SPECIMENS/DATA TO RESEARCH COLLABORATORS OUTSIDE PARTNERS**

Specimens or data collected by Partners investigators will be sent to research collaborators outside Partners, indicate to whom specimens/data will be sent, what information will be sent, and whether the specimens/data will contain identifiers that could be used by the outside collaborators to link the specimens/data to individual subjects.

Serum will be sent to [name] and [name] at the NIH for analysis of INSL-5 levels in girls with anorexia nervosa for a collaborative study. All samples and clinical data will be coded so that only the study staff at MGH can link the identities. The NIH researches will only receive coding to link the samples with the clinical data and will not receive any subject-specific identifying information. The clinical data associated with the samples will include anthropometric and menstrual information.

Specifically address whether specimens/data will be stored at collaborating sites outside Partners for future use not described in the protocol. Include whether subjects can withdraw their specimens/data, and how they would do so. When appropriate, submit documentation of IRB approval from the recipient institution.

No data and specimens collected at MGH will be stored at other sites.

### **RECEIVING SPECIMENS/DATA FROM RESEARCH COLLABORATORS OUTSIDE PARTNERS**

When specimens or data collected by research collaborators outside Partners will be sent to Partners investigators, indicate from where the specimens/data will be obtained and whether the specimens/data will contain identifiers that could be used by Partners investigators to link the specimens/data to individual subjects. When appropriate, submit documentation of IRB approval and a copy of the IRB-approved consent form from the institution where the specimens/data were collected.

Subjects who do not live locally will be able to have their blood drawn in a local laboratory for levels of IGF-1 and bone markers, these results and/or specimens will be sent to MGH.

Effects of Anorexia Nervosa on Peak Bone Mass

NCT01301183

Version date: March 29, 2018

Analytical Plan

ANALYTIC PLAN

[name]., a Professor of Biostatistics at Harvard Medical School and co-investigator, has co-authored papers with us for more than 20 years and has been instrumental in our study design and will analyze these data. Data generated will be largely longitudinal. Measures of hormone function, bone turnover markers, nutrition, activity, body composition, bone density, bone microarchitecture and strength will be collected every three to six months for 12 months. There are three study groups: AN randomized to rhIGF-1 and transdermal estrogen, estrogen alone with placebo, and normal adolescents. Randomization will be performed by the MGH Research Pharmacy.

Analysis and interpretation are listed below for each aim and sub-aim:

Sample Size Determination: The study is powered to our primary endpoints, (i) change in lumbar spine BMD (specific Aim 1A), and (ii) change in trabecular bone density (specific Aim 3A) in girls with AN who receive estrogen and rhIGF-1 versus estrogen alone. **Specific Aim 1A:** The primary analysis for this Specific Aim and the study is to compare the change in BMD over time in subjects with AN randomized to receive rhIGF-1 and estrogen (n=50) with the corresponding change in estrogen treated subjects (n=50). Using data from our previous study, we found that the variance covariance matrix of the random effects model was as follows: variance-intercept 0.01056, variance-slope 0.001523, covariance -0.001, and the residual variance around each subject's trajectory 0.000533. Based on these parameters, with 100 subjects with AN (50 in each group), we will have an 80% chance of detecting a significant (p=0.05 two sided) difference in change in lumbar spine BMD between girls who receive estradiol and rhIGF-1 versus estradiol alone if the true difference in slope between the groups is 0.03 g/cm²/year. This is a medically significant difference in that lumbar spine BMD in adolescents with AN is about 0.08 g/cm² lower than that in healthy adolescents at baseline. Estradiol alone has a net effect of 0.02 g/cm².year in increasing bone density, so an additional effect of 0.03 g/cm² (with rhIGF-1) added to 0.02 g/cm² (from estradiol alone) would be a net effect of 0.05 g/cm²/year (from estradiol and rhIGF-1). This would allow girls with AN to catch up to healthy adolescents. The sample size calculation, which assumes a 20% dropout rate, is based on the methods described by Yi and Panzarella (38) using the program <http://hedwig.mgh.harvard.edu/biostatistics/node/35>. The same model can be used with covariates and possible mediators of treatment effects such as baseline nutritional status, body composition, hormonal status, exercise and pubertal maturation. We will also explore the possibility that effects of rhIGF-1 with estradiol persist after discontinuation of treatment by examining bone density 12 months after stopping therapy.

Specific Aim 1B. We will analyze the impact of rhIGF-1 with estrogen (n=50) versus estrogen alone (n=50) on levels of the bone turnover markers, PINP and CTX, in girls with AN at 3, 6, 9 and 12 months using a repeated measures ANOVA. The primary planned analysis will be the difference in mean levels by treatment group during the 3, 6, 9 and 12 month observations. As for Specific Aim 1A, we will examine whether effects of combination therapy persist following discontinuation of therapy by examining these markers after 12 months of stopping therapy.

Specific Aim 1C. We will use the longitudinal model described above to compare the rate of bone mass accrual in girls with AN who receive rhIGF-1 with estrogen (n=50) with that seen in healthy controls (n=36). We expect the change in BMD in AN girls to exceed that in controls because of a “catch up” effect when rhIGF-1 is used with estradiol. We will control for multiple comparisons in our analysis when comparing against controls. Both unadjusted and multiplicity adjusted analyses will be presented.

Specific Aim 2A. In a cross-sectional design, we will compare the described HR-pQCT endpoints and bone strength (as assessed by FEA) in girls with AN (n=100) to those in healthy adolescents (n=36). We will use the Student t test when variables are normally distributed or when transformations can be performed to approximate a normal distribution; otherwise, we will use non-parametric tests such as the Wilcoxon rank sum test. Our preliminary data indicate lower trabecular bone density in 8 girls with AN compared with 6 controls (162 ± 27 vs. 209 ± 36 g/cm³, $p=0.02$). Based on these data, with 100 girls with AN and 36 controls in the study, we have >99% power for detecting a significant difference in trabecular bone density between the groups at an alpha level of 0.05. Another component of this specific aim is to determine the extent to which DXA parameters and possibly clinical parameters predict bone microarchitecture in the 100 adolescents with AN. This will help elucidate the role of DXA in the future clinical evaluation of adolescents with AN. Linear regression followed by regression modeling will be performed to determine hormonal, body composition, nutritional and exercise predictors of bone microarchitecture and bone strength in girls with AN and healthy adolescent girls.

Specific Aim 2B. The goal of this specific aim is to determine prospectively changes in bone microarchitecture and bone strength in girls with AN who receive rhIGF-1 and estrogen therapy (n=50) compared with changes in AN receiving estrogen alone (n=50). Bone microarchitecture will be assessed using HR-pQCT and bone strength using FEA at baseline, six, 12 and 24 months of the study. Our second primary study endpoint is the change in trabecular bone density in the two treatment groups over the course of the study. With 100 subjects (50 in each group) we will have an 80% chance of detecting a significant difference ($p=0.05$ two sided) in change in trabecular bone density in girls with AN who receive rhIGF-1 and estrogen compared with estrogen alone if the true relative change is 3.5% over the 12 month period. This assumes a standard deviation of relative change of 6%, as was found in the group of AN women who gained weight in a study by Milos *et al* (39). To understand the clinical meaning of such a change we note that AN women had a 20% decrease in trabecular bone density compared to normal women. The analysis will be accomplished using a longitudinal mixed model ANOVA with a random patient and time (slope) effect. The measure of interest will be the group time interaction. We estimate a 20% dropout rate based on our previous study. A secondary analysis will be a joint model with weight gain as described for Specific Aim 1. We will also compare changes in total cross-sectional area, cortical thickness, TbN, TbTh and TbSp between AN receiving rhIGF-1 and estrogen with AN receiving estrogen alone. Although this is not a specific aim, it will be interesting to compare the changes in BMD with the change in bone strength. An issue is that BMD and bone strength are measured in different units. In order to make the comparisons understandable, we will transform both to percent predicted using the data from healthy adolescent girls. Then we will fit a joint model for both measurements to assess the relationship between the two and which measure is affected most by treatment. In addition, we will examine these endpoints 12 months after stopping therapy to determine whether effects persist after discontinuing combination therapy. When comparing with healthy adolescent girls, we will adjust for multiple comparisons. Both unadjusted and multiplicity adjusted analyses will be presented.

Specific Aim 2C. The random effects model can also be used where the “treatment” variable is replaced by a continuous variable such as IGF-1 level. There are two possible analyses for this Specific Aim. One analysis would use all randomized subjects, and this would be very similar to the analysis for the treatment effect except that it may be more powerful if there is a large variation in IGF-1 levels in response to treatment with rhIGF-1. The other is to restrict analysis

to the group receiving IGF-1 to test whether the effect of treatment on bone microarchitecture parameters and bone strength is associated with the IGF-1 level. We will control for effects of nutrition, pubertal status, hormonal status (including estradiol and leptin), calcium metabolism and exercise in this analysis. As in most clinical trials, there will be measurements made during the trial of parameters which may or may not mediate the treatment effect. For instance we do not expect short term changes in nutritional status, weight, and hormonal status to affect the difference between treatment effects of estrogen versus rhIGF-1 plus estrogen on BMD or bone strength but we may find the bone turnover markers such as P1NP do mediate the effect of treatment. Mediation analysis in longitudinal trials is difficult and requires strong assumptions. We will explore mediation using the framework described by Ditlevsen *et al* (40).

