- (j) Activity Assessment: Habitual exercise and activity will be assessed using a standardized exercise questionnaire, which provides a good estimate of past year physical activity in adolescents (26, 27). (All subjects consent to the activity assessment, although it is treated as optional during the study.)

(k) Two subtests, Vocabulary and Matrix Reasoning, from the Weschler Abbreviated Scale of Intelligence (WASI), a Color-Word Interference Test subtest from the Delis Kaplan Executive Functioning Scale (DKEFS), and the California Verbal Learning Test (CVLT). (All subjects consent to the cognitive assessments, with the intention that they will be completed to the extent that time, subject schedule, and circumstances allow during the visit)

6-month and 12-month (AN Subjects Only): will include all the baseline procedures but the bone age x-ray.

Eligible consented subjects will be allowed to have CT scans performed between the screening and baseline visits if scheduling conflicts arise with the baseline visit. This will allow the subject to obtain a baseline assessment of bone microarchitecture prior to the initiation of rhIGF-1 supplementation. In the event that a CT cannot be performed on the scheduled baseline visit date due to unforeseen issues, willing subjects will be able to return within a 1 week window for this test. DXA scans can also be completed at screening visit if not able to be performed at baseline visit. MR/MRS will be repeated at 12 month visit for patients with anorexia nervosa. We will also repeat the Pref-1 levels for those who enrolled in this optional part of the study.

1-month, 4.5-month, 7.5-month and 10.5 month visits (AN Subjects Only): Evaluations on these visits will include:

- (a) History and physical exam, including height and weight
- (b) Pregnancy test
- (c) Serum IGF-1 and glucose

3-month and 9-month visits (AN Subjects Only): Evaluations on these visits will include:

- (a) History and physical exam, including height and weight
- (b) Pregnancy test
- (c) Serum IGF-1 and glucose
- (d) Nutrition evaluation will be assessed by using 4-day food records for macro- and micronutrient intake (Nutrition Data Systems, version 4, Minneapolis, MN)
- (e) Activity assessment: Habitual exercise and activity will be assessed using a standardized exercise questionnaire. (All subjects consent to the activity assessment, although it is treated as optional during the study.)
- (f) Bone turnover markers and hormones

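### The 80% power for Aim 1A under 20% dropout is reached only under some readings of the plan; a common baseline mean for the two randomised arms would add about 3 points without extra patients

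*SAP*

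**What the plan says.** The SAP, under Sample Size Determination (Specific Aim 1A), names the comparison of BMD change between the two randomised AN arms as the primary analysis of the study. With 50 girls per arm and a two-sided 0.05 level it states that "we will have an 80% chance of detecting a significant" difference "if the true difference in slope between the groups is 0.03 g/cm²/year". The inputs are listed as "variance-intercept 0.01056, variance-slope 0.001523, covariance -0.001", with a residual variance of 0.000533. It adds: "The sample size calculation, which assumes a 20% dropout rate".

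Aim 1A calls the model only a random effects model. The nearest fuller description is under Specific Aim 2B: a mixed model with random patient and slope effects, where "The measure of interest will be the group time interaction". Neither section says whether the two arms share a baseline mean.

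For the scan times, the protocol lists DXA among the baseline procedures and then states: "6-month and 12-month (AN Subjects Only): will include all the baseline procedures but the bone age x-ray". The itemised 3- and 9-month visits include no DXA. The opening paragraph of the SAP says more loosely that a mixed list of measures, bone density among them, is collected every three to six months.

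**The concern.** Most of the inputs to the power figure are printed, so it can be checked. On the natural reading (three DXA visits, a group-by-time slope model with a separate baseline mean for each arm, 20% lost) none of the dropout patterns tried reaches 80%.

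What is at stake is modest. The figure supports the sample size of the study's primary analysis, and leaving the baseline handling open allows two different primary models whose power differs by about 3 points. Randomisation justifies the more efficient of the two, and it needs no new data.

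**Working it through.** **Inputs.** From the SAP, Aim 1A: intercept variance 0.01056, slope variance 0.001523, covariance -0.001, residual variance 0.000533, 50 per arm, difference 0.03 g/cm²/year, two-sided 0.05, 20% dropout (10 per arm). From the protocol: DXA at t = 0, 0.5 and 1 year. Assumed, because not stated: when the 10 dropouts per arm leave.

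**Method.** Each girl's BMD vector has covariance V = ZDZ' + σ²I, where Z holds an intercept and time, D holds the random-effect variances and covariance, and σ² is the residual variance. The information for the fixed effects is the sum of X'V⁻¹X over all girls, using the scans each one has. SE is the standard error of the group-by-time coefficient. Power = Φ(0.03/SE − 1.96), and the difference detectable with 80% power is 2.80 × SE.

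**Check by hand, no dropout.** With three equally spaced visits, Σ(t − mean)² = 0.25 + 0 + 0.25 = 0.5. The variance of one girl's fitted slope is 0.001523 + 0.000533/0.5 = 0.002589 (SD 0.0509). The SE of the difference is √(2 × 0.002589/50) = 0.01018. Power = Φ(0.03/0.01018 − 1.96) = Φ(0.99) = 83.8%. So 50 per arm exceeds 80% before dropout.

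**With 20% dropout, separate baseline mean per arm:**

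| Dropout pattern | SE | Power | Detectable difference | n per arm for 80% |
|---|---|---|---|---|
| All after month 6 | 0.01078 | 79.5% | 0.0302 | 51 |
| Half before, half after | 0.01102 | 77.7% | 0.0309 | 53 |
| All before month 6 | 0.01128 | 75.8% | 0.0316 | 56 |

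Using t rather than normal quantiles lowers each power by about 0.8 points.

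**Same patterns, common baseline mean** (no group effect at time 0):

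| Dropout pattern | SE | Power | Gain (points) | n per arm for 80% |
|---|---|---|---|---|
| All after month 6 | 0.01034 | 82.6% | 3.1 | 47 |
| Half before, half after | 0.01061 | 80.7% | 3.0 | 50 |
| All before month 6 | 0.01090 | 78.6% | 2.8 | 52 |

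**What the gain rests on.** A negative intercept-slope covariance means that the observed baseline carries information about the slope. With the covariance set to 0 and the half/half pattern, power is 77.4% with separate means and 77.8% with a common mean, a gain of about 0.4 points. At covariance 0 none of the three patterns reaches 80% under either model.

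**Other readings.** Three-monthly BMD with gradual dropout and separate baselines gives 81.8%.

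**The case against.** A reader might infer that the SAP's 80% is an arithmetic error. The documents do not support that, for three reasons.

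- The SAP does not give every input. Dropout timing, the BMD times entered in the power program and the baseline handling are all unstated, and the cited program could not be run here. A common baseline with half/half dropout gives 80.7%, so the stated figure may already rest on the model recommended below. Three-monthly measurement gives 81.8%; the protocol's visit list contradicts that schedule, but the program may still have used it.
- The gap is close to rounding. Late dropout gives 79.5%, and the detectable differences of 0.0302 to 0.0316 all round to 0.03.
- Uncertainty in the inputs is larger than the gap. With separate baselines, a slope variance 10% lower gives 81.7% (late dropout) or 80.1% (half/half); 10% higher gives 77.3% or 75.4%.

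All of this stands, and it limits the point to a clarification and an improvement.

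A second tempting inference is that the common baseline always restores 80%. It does not: under early dropout it gives 78.6%. A third is that Aim 2B would gain as much. That cannot be computed, because Aim 2B gives only a standard deviation of relative change and no variance components.

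The objection does not remove the case for specifying the model. The SAP leaves open a choice worth about 3 points in the primary analysis, and a reader cannot tell which version the 80% describes.

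**Conclusion.** The point holds as a minor one. With the protocol's DXA visits, the stated variance components and separate baseline means, power for 0.03 g/cm²/year under 20% dropout is about 76-79.5%, against a stated 80%. With a common baseline mean it is about 79-83%. Both ranges cover dropout timings from all before to all after month 6, which is an assumption, and both use the normal approximation. The advantage of about 3 points depends on the covariance of -0.001, an estimate from one previous study. Nothing here calls for a change in sample size, endpoint or conduct.

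**What to change.** In the SAP, under Aim 1A:

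1. Prespecify the longitudinal mixed model with a common baseline mean for the two randomised AN arms: baseline BMD stays in the outcome vector, there is no group main effect at time 0, and the treatment effect is the group-by-time slope. Limit the constraint to the randomised arms. The healthy controls in Aim 1C are not randomised and need their own baseline mean.
2. State the DXA times, the dropout pattern and the baseline handling behind the power figure.
3. Quote power as about 79-83% under 20% dropout, noting that it depends on the intercept-slope covariance. If separate baseline means are kept, quote about 76-79.5%.

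The cost is a few sentences of SAP text and one restated figure, with no additional patients, visits or data.
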